Non-Interventional Stu	dv (NIS)	Protocol
------------------------	----------	----------

Drug Substance: N/A

NIS code: NIS-ORU-IRE-2009/1

Version No.: 4.0

Date: 8 December 2009

Epidemiological study to describe NSCLC clinical management patterns in Central Eastern Europe and Russia. Lung-EPICLIN

Sponsor:

AstraZeneca [name]

[contact] [contact]

The following Amendment(s) and Administrative Changes have been made to this Non-Interventional Study Protocol, since the date of preparation:

Amendment No.	Date of Amendment	Local Amendment No.	Date of Amendment	
		Addendum for Russia	08.12.2009	
Administrative change No.	Date of Administrative Change	Local Administrative change No.	Date of Administrative Change	

This submission /document contains trade secrets and confidential commercial information, disclosure of which is prohibited without providing advance notice to AstraZeneca and opportunity to object.

Version No: 4.0 Date: 8 December 2009

SUMMARY OF THE NON-INTERVENTIONAL STUDY PROTOCOL

Epidemiological study to describe NSCLC clinical management patterns in Central Eastern Europe and Russia. Lung-EPICLIN

National Coordinators

[name] Russian Cancer Research Center Department of Clinical Pharmacology and Chemotherapy [name]

[contact]

Protocol of Non-Interventional Study

Drug Substance: N/A

NIS Code: NIS-ORU-IRE-2009/1

Version No: 4.0 Date: 8 December 2009

Number of patients, sites and Countries (planned) in the study

It is estimated that 500 patients will be entered into the study from all over Russia.

Total planned study period

Estimated first patient in: 1st February 2010

Estimated last patient in: 1st August 2010

Estimated last patient out: 1st August 2011

Estimated database lock: 1 st October 2011

Medicinal product (type, dose, mode of administration) and concomitant medication (if applicable)

This is a purely observational study; therefore patients are not assigned to a particular therapeutic strategy beforehand by a protocol. Treatment will be according to current clinical practice.

Overall Aim for this Non-Interventional Study (NIS)

To provide accurate, reliable information on NSCLC clinical management across Central Eastern European countries and Russia in order to detect unmet medical needs of this disease in terms of:

- Patient and hospital characteristics.
- Diagnostic and treatment approaches: initial and subsequent.
- Follow-up patterns in clinical management.
- Outcomes: symptoms, death, functionality, quality of life.
- Use of resources and burden on patients and health care systems.

Study Objectives

a. Descriptive objectives:

Regarding the patient and the disease

- To describe NSCLC patient characteristics.
 - o Demographics.
 - o Co-morbidities and relevant medical history.
 - o Disease-related habits.

Protocol of Non-Interventional Study Drug Substance: N/A

NIS Code: NIS-ORU-IRE-2009/1

Version No: 4.0 Date: 8 December 2009

- To describe the disease at baseline.
 - o Location, tumour type, stage, extent, mutation of biological markers.
 - o Related symptoms.
- To describe patient outcomes.
 - o Performance Status/ECOG.
 - Therapy outcomes and related events.
 - Disease progression.
 - o Death.
 - O Quality of life and functional status.

Regarding clinical management

- To describe hospital characteristics.
 - Size and type.
- To describe the diagnostic patterns of the disease.
 - Tests performed.
 - o Patient flow-chart until final diagnosis.
- To describe NSCLC treatment received.
 - Surgery.
 - o Radiotherapy.
 - o Chemotherapy.
 - o Other.
- To describe any other use of health care resources.
 - Emergency visits.
 - Hospital stays.
 - Primary care visits.

Protocol of Non-Interventional Study Drug Substance: N/A

NIS Code: NIS-ORU-IRE-2009/1

Version No: 4.0 Date: 8 December 2009

- o Outpatient therapy.
- o Home care.

b. Analytical objectives:

- To assess the differences in patient characteristics, disease stage (differentiating between non-advanced disease, locally advanced disease, metastatic disease), and in clinical management across Central Eastern European countries and Russia.
- To detect differences in clinical outcomes and related factors among participating countries.
- To identify factors associated with clinical outcomes (patient, disease stage -see above- and clinical management related factors): predictive modelling for improved patient outcome.
- To identify factors associated with the different levels of functional status and quality of life.
- To compare the use of health care resources among countries.

Study design

Multinational, multicentre, non-interventional, prospective cohort study.

[figure not shown]
Protocol of Non-Interventional Study

Drug Substance: N/A

NIS Code: NIS-ORU-IRE-2009/1

Version No: 4.0 Date: 8 December 2009

Study Flow-chart

Patient population

All NSCLC patients attending the responsible department of treating this type of patients (e.g. Oncology Department, Pulmonology Department) for the first time (regardless of whether the patient is diagnosed with locally, advanced or metastatic disease) at the participating sites

Version No: 4.0 Date: 8 December 2009

from the first of January 2010 to the end of July 2010. Patients diagnosed, or even treated, in other departments within the same hospital or in another hospital are susceptible to be included in the study if full access to the patient's medical record is made available.

Methods

The inclusion period will last 6 months, from the 1st of February 2010 to the 1st of August 2010. All patients attending the responsible department of treating this type of patients for the first time during this period should be included in the study. Patients could be retrospectively included in case of not receiving the Ethics Committee approval by the first of January 2010, but only those patients attending for the first time during the enrolment period.

The follow-up period will last for at least one year (the follow-up period will be conducted until the end of July 2011, so the maximum follow-up period will comprise 18 months) or until the patient is deceased, lost to follow-up or changed to another hospital.

Information regarding patients and disease characteristics as well as clinical management approach (diagnostic methods, treatments and follow-up patterns) and final outcomes will be taken from the medical record at each evaluation visit. These visits will be performed according to normal clinical practice.

Functional status and Quality of Life (QoL) questionnaires will be collected directly from the patients immediately after obtaining informed consent.

All patients regardless of whether they are participating in clinical trials or not are eligible to be included in the study. This is a purely observational study, therefore participation in this study will not interfere with participation in a clinical trial.

Statistical Analysis

A descriptive analysis approach will be used to analyse NSCLC population, clinical management, clinical outcomes and use of health care resources.

Version No: 4.0 Date: 8 December 2009

TABLE OF CONTENTS

PAGE

SUMMA	RY OF THE NON-INTERVENTIONAL STUDY PROTOCOL	2
TABLE (OF CONTENTS	8
LIST OF	ABBREVIATIONS AND DEFINITION OF TERMS	11
1.	INTRODUCTION	13
1.1	Background and rationale	13

Appendix A Signatures

Appendix B EQ-5D Questionnaire

Appendix C FACT-L Questionnaire

Date: 8 December 2009

Version No: 4.0 Date: 8 December 2009

LIST OF ABBREVIATIONS AND DEFINITION OF TERMS

The following abbreviations and special terms are used in this Non-Interventional Study Protocol.

Abbreviation or special term	Explanation
AE	Adverse event (see definition in Section 4.4.1)
AZ	AstraZeneca
BSC	Best Supportive Care
CRA	Clinical Research Associate
CRF	Case Report Form
CRO	Clinical Research Organisation
CT-Scan	Computerized Tomography Scan
ECRF	Electronic Case Report Form
ER	Emergency Room
EWB	Emotional well-being
Ethics Committee	Synonymous to Institutional Review Board and Independent Ethics Committee
FACT-L	Functional Assessment of Cancer Therapy - Lung
FNAB	Fine Needle Aspiration Biopsy
FWB	Functional well-being
GCP	Good Clinical Practice
GLM	General Linear Models
ICF	Informed Consent Form
International Co-ordinating investigator	If a study is conducted in several countries the International Co-ordinating Investigator is the investigator co-ordinating the investigators and/or activities internationally
ICU	Intensive Care Unit
NSCLC	Non-Small Cell Lung Cancer
Outcome variable	A variable (usually a derived variable) specifically defined to be used in the analysis of a study objective
PWB	Physical well-being
PET	Positron Emission Tomography
Principal investigator	A person responsible for the conduct of a clinical study at an investigational

Date: 8 December 2009

Abbreviation or special term	Explanation
	study siteEvery investigational study site has a principal investigator
PRO	Patient-Reported Outcomes: Umbrella term categorising all types of subjective reported outcomes such as health-related quality of life, treatment satisfaction, subjective health status and subjective symptoms
PS	Performance Status
QoL	Quality of Life
RECIST	Response Evaluation Criteria in Solid Tumours
SCLC	Small Cell Lung Cancer
SWB	Social well-being

Version No: 4.0 Date: 8 December 2009

1. INTRODUCTION

1.1 Background and rationale

Lung cancer is one of the leading causes of death worldwide. Of the 7.3 million deaths caused by cancer every year, 17% are due to Lung Cancer. Prevalence of this disease during 2006 alone in Europe was 386,300 total cases, and 334,800 died during the same period¹.

Of the entire lung cancer population, Non-Small Cell Lung Cancer (NSCLC) is the most common (around 80%) compared with Small Cell Lung Cancer (SCLC)². Squamous Cell Lung Cancer and Adenocarcinoma are the most common subtypes in Europe between 46.5%³-33%⁴ and 23.6%³-30%⁴ respectively.

Histopathologically confirmed lung cancer is essential for optimal management of the individual patient and must be secured before chemotherapy and radiotherapy are initiated. However, in rare cases it may be impossible to obtain tumour tissue for examination due to multiple significant co-morbidities or poor performance status. Furthermore, resources available for obtaining correct diagnosis and TNM classification are likely to differ among centres, exemplified by the lack of resources for PET examination in many sites throughout Central Eastern Europe and Russia.

According to national and international guidelines, surgery, chemotherapy and radiotherapy are the cornerstones of NSCLC treatment. Individualized supportive care should constitute an essential element in the management of all patients with NSCLC. Treatment choices are determined by the stage of the disease at each moment and the patient's individual condition (performance status, co-morbidity and age).

The median survival for patients with stage IIIB or IV disease with current first-line chemotherapy regimens is approximately 7-10 months, the one-year survival rate is 35% and response rates range between 17-37%. Once patients experience treatment failure with initial therapy, response to further systemic treatment is approximately 10% Further progress is anticipated with the novel therapeutic approach of combining existing chemotherapy with drugs that target specific signalling pathways of lung cancer progression.

Consistency of application might not be a problem for the treating oncologist within his or her own practice, but it might have significant ramifications for nursing staff, pharmacists and junior medical staff who are expected to be familiar with and deliver multiple regimens and schedules. The potential for error increases. This can be extrapolated to a larger setting. All European countries are facing common challenges for delivering appropriate, evidence-based care to patients with cancer. Despite tangible improvements in diagnosis and treatment, there are, as discussed above, marked differences in cancer survival throughout Europe. The reliable translation of new research evidence into consistent patient-oriented strategies is a key endeavour to overcome inequalities in healthcare. Clinical-practice guidelines are important tools to improve quality of care by informing professionals and patients about the most appropriate clinical practice¹⁶.

Registries are currently the main source of information on lung cancer, and in fact in clinical trials they are the main tool for making a decision on how to manage the disease. Although they are recognized as useful sources of information, cancer registries, and specifically lung cancer registries, are mainly locally based and maintained in small areas, mostly in reference hospital areas. Most of them do not include broad countrywide information and are therefore only useful at the time of preparing treatment guidelines for hospitals, but not for any decision making as regards the entire Healthcare Systems.

There are country level registries in some European countries, but they do not collect all the data necessary for making the best decision on how to manage the disease in detail and how to implement resources at different levels of the Healthcare System. The same issue with registries occurs worldwide. Most of them, such as those maintained in the United States, Canada or Australia, enjoy a good reputation but have the same lack of information as most of the European registries. The discussion above emphasizes the need for a reliable, accurate and updated multicentre Central Eastern European and Russian cohort study.

Version No: 4.0 Date: 8 December 2009

A patient-reported outcome (PRO) is the measurement of any aspect of a patient's health status coming directly from the patient, without interpretation of the patient's responses by a physician or anyone else. The use of PRO instruments is part of a general movement toward the idea that the patient, properly queried, is the best source of information about how he or she feels¹⁷.

Patients can indeed understand and report the severity of their symptoms. PROs are currently used in trials that assess the control of cancer symptoms, complementary treatment, and alternative medicine. Patient reporting is also reliable in documenting the severity of specific disease-related patient symptoms, typically by the use of a linear analogue scale. The usefulness of PROs in clinical trials is especially important in the context of modern managed health care and the 15 minute visit, which allows barely enough time to discuss the disease itself, let alone issues about symptoms. Undoubtedly, clinicians support the use of information provided by the patient on their condition as a key component of medical care¹⁹.

The lack of good, updated, organized and accessible local epidemiological data, clinical management data and knowledge of how to use healthcare resources in view of the many different treatment regimens available, all leads to an underestimation of the actual burden of lung cancer and associated unmet medical needs, with consequences for payers and health decision makers, at the national and European level, as well as for patients and society.

Currently, most investigation into lung cancer, and specially NSCLC is focused on the clinical outcomes of some treatment strategies and, in the field of epidemiology, in assessing the likely risk factors associated with the disease. There are only a few current studies on how patients are managed in real life practice²⁰⁻²⁴, these are clinical epidemiology studies. In view of this it would be very useful for physicians to be informed of treatment strategies used around Central Eastern Europe and Russia, and also to have information on the impact of these treatment options on overall costs and patient outcomes, in order to determine the best management pattern for each type of patient.

The rising costs of cancer treatments, addressing the needs of reimbursement and payer agencies are all important for gaining regulatory approval for new treatments. Governments and decision makers are struggling to provide access to new therapies against constrained health care budgets. Along with information on clinical efficacy, decision makers would benefit from data on clinical effectiveness and cost-effectiveness. The EPICLIN study is designed to provide information on the clinical effectiveness of existing products, health care resources that are associated with existing therapy and information on patients' quality of life. This is the first study to look at treatment patterns for all lines of treatment across Central Eastern Europe and Russia, identify patterns of care that may be similar or different across Central Eastern Europe and Russia, to make comparisons among treatments and countries and help in to determine effective and cost-effective treatments in the real world.

2. OBJECTIVES OF THE NON-INTERVENTIONAL STUDY

The overall aim of the study is:

To provide accurate and reliable information regarding NSCLC clinical management across Central Eastern European countries and Russia in order to detect unmet medical needs of this disease in terms of:

- Patient and hospital characteristics.
- Diagnostic and treatment approaches: initial and subsequent.
- Follow-up patterns in clinical management.
- Outcomes: symptoms, death, functionality, quality of life.
- Use of resources and burden on patients and health care systems.

2.1 Objectives

2.1.1 Descriptive objectives

Regarding the patient and the disease

- To describe NSCLC patient characteristics.
 - Demographics.
 - o Co-morbidities and relevant medical history.
 - Disease-related habits.
- To describe the disease at baseline.
 - o Location, tumour type, stage, extent, mutation of biological markers.
 - o Related symptoms.
- To describe patient outcome.
 - Performance Status/ECOG.
 - Therapy outcomes and related events.
 - Disease progression.
 - o Death.

Protocol of Non-Interventional Study Drug Substance: N/A

NIS Code: NIS-ORU-IRE-2009/1

Version No: 4.0 Date: 8 December 2009

o Quality of life and functional status.

Regarding clinical management

- To describe hospital characteristics.
 - Size and type.
- To describe the diagnostic patterns of the disease.
 - Tests performed.
 - o Patient flow-chart until final diagnosis.
- To describe NSCLC treatment received.
 - o Surgery.
 - o Radiotherapy.
 - o Chemotherapy.
 - o Other.
- To describe any other use of health care resources.
 - Emergency visits.
 - Hospital stays.
 - Primary care visits.
 - Outpatient therapy.
 - Home care.

2.1.2 Analytical objectives

- To assess the differences in patient characteristics, disease stage (differentiating between non-advanced disease, locally advanced disease, metastatic disease), and in clinical management across Central Eastern European countries and Russia.
- To detect differences in clinical outcomes and related factors among countries.
- To identify factors associated with clinical outcomes (patient, disease stage –see above- and clinical management related factors): predictive modelling for improved patient outcome.

Version No: 4.0 Date: 8 December 2009

- To identify factors associated with the different levels of functional status and quality of life.

- To compare the use of health care resources among countries.

3. STUDY PLAN AND PROCEDURES

3.1 Overall study design and flow chart

This is a multinational, multicentre, non-interventional, prospective cohort study to be carried out in a representative selection of hospitals in order to assess lung cancer management in countries throughout Central Eastern Europe and Russia. Within the scope of this study, no diagnostic or monitoring procedures in addition to the routine procedure will be applied to the patients.

To ensure a valid picture of real life management, sites will be selected focusing on representative hospitals where lung cancer patients are being managed, in all participating countries.

All NSCLC patients attending the responsible department of treating this type of patients (e.g. Oncology Department, Pulmonology Department) for the first time (regardless of whether the patient is diagnosed with locally, advanced or metastatic disease) at the participating sites from the first of January 2010 to the end of July 2010. Patients diagnosed, or even treated, in other departments within the same hospital or in another hospital are susceptible to be included in the study if full access to the patient's medical record is made available.

Patients could be retrospectively included in case of not receiving the Ethics Committee approval by the first of January 2010, but only those patients attending for the first time during the enrolment period.

Information regarding patient and disease characteristics will be taken from the medical record, as well as management approaches regarding the visit plan, diagnostic tests performed and therapies received by the patient.

A sample of patients will be invited to complete Quality of Life questionnaires when coming to the responsible department of treating this type of patients for assessment. PROs will be collected at each evaluation visit from the first visit (diagnosis) to last visit (after 12 months). PROs will not be completed at treatment administration visits and/or disease- or treatment-related event visits.

The data source for this study will be the medical record at the responsible department of treating this type of patients for each patient. Neither visits nor interventions will be carried out for the study purposes.

Protocol of Non-Interventional Study Drug Substance: N/A

NIS Code: NIS-ORU-IRE-2009/1

Version No: 4.0 Date: 8 December 2009

The eCRF will be completed at each evaluation visit, entering information on this visit and any other relevant data related to any intermediate visits between the last evaluation visit and the current visit. The study termination module of the eCRF must be completed at the time the investigator is aware of patient's death or withdrawal.

Figure 1 Study flow chart

[figure not shown]

Table 1 Study plan

Time	Inclusion assessment	Each evaluation visit
Informed Consent (when necessary)	X	
Patient Demographics	X	
Site information*	X	
Smoking habits	X	
Disease Information	X	X
Diagnosis information	X	
Therapy information	X	X
Clinical outcomes		X
Events due to therapy and/or disease		X
Adverse events due to therapy		X
Use of resources	X	X
Patient Reported Outcomes (a sample of patients)	X	X

Version No: 4.0 Date: 8 December 2009

Time	Inclusion assessment	Each evaluation visit
Study termination (when investigator is aware)		X

^{*}At the time of registering a participating site

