3.3.2 Patient population selection criteria

All patients with NSCLC attending participating hospitals during the pre-specified period will be eligible to participate in the study.

Patients will be asked to sign an informed consent form which specifies that there will be no change in clinical management because of the study and that it only involves collecting information[†]

All patients regardless of whether they are participating in clinical trials or not are eligible to be included in the study. This is a purely observational study, therefore participation in this study will not interfere with participation in a clinical trial. The participation in this study will not prevent the patient from being given the opportunity of receiving an investigational product or participating in another study.

A sample of patients (25% of the whole sample) will be asked to complete Quality of Life questionnaires when attending the programmed assessment visits to the physician. Only patients who are not participating in clinical trials will be asked to participate in the Quality of Life sub-study. These patients will be asked to sign a specific informed consent form.

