3.3.2.1 Inclusion Criteria

For inclusion in the study, patients must meet all of the following criteria:

- 1. Confirmed NSCLC diagnosis (e.g. bronchoscopic biopsy or FNAB), all stages, men and women, attending the responsible department of treating this type of patients for the first time between January 1st, 2010 and August 1st, 2010.
- 2. For PRO sub-sample: ability to read and write since they will be asked to participate in the PRO part of the study. Selection will not be based on the disease stage of each patient, in order to avoid a selection bias.
- 3. 18 years of age or more.

-

[†] Only when required by local authorities.

Version No: 4.0

Date: 8 December 2009

3.3.2.2 **Exclusion Criteria**

According to the study design there will not be any exclusion criteria in order to provide a high external validity and to obtain the most accurate real daily practice information.

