6.3 Method of statistical analysis

Considering the study objectives, the analysis strategy will be as follows:

A descriptive analysis approach will be used to analyse NSCLC population, clinical management, clinical outcomes and health care resources.

Descriptive statistics will include frequency tables (n, mean, median, standard deviation, minimum and maximum for continuous variables and n, frequency and percentage for categorical values).

The assessment of different associations will be as follows:

Logistic and general linear models (GLM) will be used to assess the association of patient characteristics (including stage of disease, histology, PS, etc) and clinical management (independent variable) with clinical outcome variables (clinical evolution, treatment related events, mortality). The interest will separately focus on the treatment differences between each of them or a group of them used. Model-based point estimates of odds ratios and corresponding 95% confidence intervals will be reported (when applicable). P-values will be reported for comparisons between different treatments.

A descriptive analysis approach will be used to assess factors related with the use of health care resources, and a comparison of the level of use of health care resources will also be made.

The assessment of quality of life will be as follows:

Changes in FACT-L total score from first visit to the visit prior to a specific treatment response with focus on treatment differences. This is a variable of particular interest and will be analysed using an ANCOVA model.

Changes in FACT-L total score from first visit to each assessment will be analysed using an ANCOVA model.

Version No: 4.0 Date: 8 December 2009

Changes in EQ-5D total score from first visit to the visit prior to a specific treatment response with focus on the differences between treatments. This is a variable of particular interest and will be analysed using an ANCOVA model.

Changes in EQ-5D total score from first visit to each assessment will be analysed using an ANCOVA model.

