8.3.1 Informed Consent requesting procedures

Informed consent must be given by all patients willing to participate in the study, if required in local regulations.

Version No: 4.0 Date: 8 December 2009

The principal investigator(s) at each centre will ensure that the patient participating in the study is given full and adequate oral and written information about the nature, purpose, possible risk and benefit of the study. Patients must also be notified that they are free to withdraw from the study at any time. The patient should be given the opportunity to ask questions and allowed time to consider the information provided.

The patient's signed and dated informed consent must be obtained before conducting any activities related with the study.

The principal investigator(s) must keep the original, signed Informed Consent Form. A copy of the signed Informed Consent Form must be given to the patient.

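### The first-visit score that serves as baseline for FACT-L and EQ-5D treatment comparisons is not a pre-treatment score for every patient, nor for later therapy lines

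*Protocol*

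**What the plan says.** On timing, Section 3.1 states: "PROs will be collected at each evaluation visit from the first visit (diagnosis) to last visit (after 12 months". Table 1 places the questionnaires at the inclusion assessment and at each evaluation visit. The Methods part of the Summary adds that "questionnaires will be collected directly from the patients immediately after obtaining informed consent".

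On who may enter, the Summary (Patient population) and Section 3.1 define entry by first attendance at the responsible department. Both state: "Patients diagnosed, or even treated, in other departments within the same hospital or in another hospital are susceptible to be included in the study", on condition of full access to the medical record. Section 3.1 also allows late entry: "Patients could be retrospectively included in case of not receiving the Ethics Committee approval by the first of January 2010".

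On the PRO sub-sample, Section 3.3.2.1 adds one criterion: "For PRO sub-sample: ability to read and write since they will be asked to participate in the PRO part of the study". Sections 3.3.2 and 4.1.3 also leave out clinical-trial participants, and Section 3.3.2 requires separate consent: "These patients will be asked to sign a specific informed consent form". Section 8.3.1 sets the order of events: "The patient's signed and dated informed consent must be obtained before conducting any activities related with the study".

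On analysis, Section 6.3 lists four quality-of-life analyses, all of change from the first visit and all by ANCOVA. One of them reads: "Changes in FACT-L total score from first visit to each assessment will be analysed using an ANCOVA model". Two others, one for FACT-L and one for EQ-5D, run to the visit before a given treatment response. These two are aimed at differences between treatments and are singled out as being of special interest.

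**The concern.** A change score compared between treatments is interpretable when each patient's starting score precedes the treatment in question. The protocol assumes this by equating the first visit with diagnosis, but its own entry rules allow a first visit that comes well after diagnosis and after therapy has begun. Such a starting score may already carry part of the benefit or toxicity of the therapy, so the later change understates it. If this is more common under one treatment than another, the comparison shows a difference that comes from timing alone.

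Later lines raise a second problem. Section 3.2 presents the study as covering all lines of treatment and names comparison among treatments as a purpose. For a second- or third-line response, the score at first attendance is not the score from which that line started.

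**Working it through.** The plan gives no figure on this point, so there is none to reproduce. The check sets the rules side by side and then illustrates a possible size.

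**Step 1: patients treated elsewhere.** Entry depends on first attendance at the department, and prior treatment in another department or hospital is no bar. The PRO conditions (literacy, own consent, no clinical-trial participation) do not remove these patients. A patient who arrives already on the therapy being compared therefore has a first questionnaire after that therapy began. For this group the point follows directly from the text.

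**Step 2: retrospectively included patients.** Consent must come before any study activity, and the questionnaires follow consent. A retrospectively included patient who joins the PRO sub-sample therefore completes the first questionnaire after the true first attendance. Whether therapy has started by then is not stated. Nor is it stated whether such patients are invited into the sub-sample, although nothing excludes them. For this group the problem is possible, not certain.

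**Step 3: later lines.** Section 6.3 keeps the first visit as the starting point whichever line produces the response. For a second- or later-line response, the change covers the earlier lines, the progression that ended them and the line of interest together. This applies even to patients untreated at entry, so it does not depend on the share who arrive treated.

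**Step 4: illustration of size for Steps 1 and 2.** The protocol gives neither the share of PRO patients already treated nor the score shift, so both are assumed.

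- s: shift of an on-treatment first score from the pre-treatment score, in FACT-L points (assumed 2, 5 or 8).
- fA, fB: share of such patients in treatment groups A and B (assumed).
- True course and final scores are taken as equal in the two groups, and the shift is not repeated after the first questionnaire.

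Artefact in the between-treatment difference in mean unadjusted change = s × (fB − fA).

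| s | 10% vs 30% | 20% vs 50% | 30% vs 30% |
|---|---|---|---|
| 2 | 2 × 0.20 = 0.4 | 2 × 0.30 = 0.6 | 0 |
| 5 | 5 × 0.20 = 1.0 | 5 × 0.30 = 1.5 | 0 |
| 8 | 8 × 0.20 = 1.6 | 8 × 0.30 = 2.4 | 0 |

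**Step 5: the planned model.** With the first score as covariate and a common slope b, the ANCOVA estimate is the difference in final means minus b times the difference in first-score means. Final means are equal here and first-score means differ by s × (fB − fA), so the artefact is b × s × (fB − fA). At an assumed slope of 0.5 to 0.8, the largest entry of 2.4 becomes 2.4 × 0.5 = 1.2 to 2.4 × 0.8 = 1.9 points, and the smallest entry of 0.4 becomes 0.2 to 0.3. ANCOVA reduces the artefact, but it does not turn an on-treatment score into a pre-treatment one.

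**The case against.** The best defence is that much of this can be handled in the statistical analysis plan promised in Section 6.1, which could add prior treatment as a covariate, restrict the analysis set or define line-specific baselines. Section 6.4 also calls the sub-study descriptive, and change since first attendance is a fair description of a patient's course. This stands for the descriptive use. It does not answer Section 6.3, which fixes the first visit as the starting point and then asks for treatment differences. That rule is stated in the protocol; it is not a detail left open.

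Three stronger readings are tempting, and the documents do not support them.

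- A reader might infer that every patient treated elsewhere has a contaminated baseline. Prior treatment need not be the treatment compared: a patient operated on elsewhere who then attends oncology may complete the questionnaire before the chemotherapy under comparison starts.
- A reader might infer that all retrospectively included patients start on treatment. The protocol does not say so.
- A reader might see a conflict between a last PRO visit after 12 months and follow-up of up to 18 months. Follow-up lasts at least one year, so a last visit some time after month 12 fits, and Section 3.1 and Table 1 both collect PROs at each evaluation visit.

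**Conclusion.** The point holds in limited form. The diagnosis label in Section 3.1 does not fit the entry rules. The first-visit baseline in Section 6.3 is not a pre-treatment score for patients already on the therapy compared, and may not be for some patients included retrospectively. For second and later lines, the change from first visit mixes the line of interest with what came before it.

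The size cannot be established from the protocol. The 0.4 to 2.4 points of unadjusted change rest on assumed shifts of 2 to 8 points and assumed unequal shares. The figure shrinks under ANCOVA with a slope below 1 and vanishes if the shares are equal, although the change would then still mix two kinds of baseline. Its direction depends on which group is more often already treated and on whether the score had fallen or risen by then. The later-line problem has not been sized.

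The fault is confined to the between-treatment comparisons in the quality-of-life sub-study. It is worth correcting because the protocol singles those comparisons out and the correction is cheap.

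**What to change.** In Section 6.3, for between-treatment comparisons, define the PRO baseline as the last questionnaire completed on or before the start of the therapy line compared. Limit those comparisons to patients with such a score. Report the remaining patients, and change from first visit in the whole sub-sample, descriptively. In Section 3.1, delete the bracketed word that equates the first visit with diagnosis.

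Keep already-treated and retrospectively included patients in the PRO sub-sample, because Section 4.1.3 wants it to represent the study population. They are described, not excluded.

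No extra visits are needed, since questionnaires are already taken at each evaluation visit. Section 4.1.2 lists onset dates for chemotherapy, radiotherapy and other therapy. For surgery it lists only whether it was performed and for what purpose, so a surgery date would have to be added to the form or taken from the medical record. The main cost is fewer patients in the treatment comparisons. The number lost cannot be given, because the protocol does not state how many patients arrive already treated.
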